## 9. Change from baseline in serum magnesium at baseline and after 12 and 26 weeks

### Safety Variables

1. All-cause mortality
2. Cardiovascular death
3. Non-fatal myocardial infarction (MI)
4. Stroke
5. Acute kidney injury (defined as doubling of serum creatinine based on the RIFLE criteria ).
6. Adverse events (AEs) and serious adverse events (SAEs). Of special interest are events including diabetic ketoacidosis (DKA), volume depletion (defined as hypotension, syncope, orthostatic hypotension or dehydration), hypoglycemic events and urinary tract infections.

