**Schedule of Assessments:**

Visit		2	3	4	5	6	7	8	9
Screening	Randomization (Discharge) c								
Week	0	0	2	6	8	12	16	20	24
Clinic / CTSA Visit		X	X	X		X		X	X
Phone Visit					X		X		X
Sign Informed Consent	X								
Medical History	X								
Weight, BMI	X	X		X		X		X	X
Physical Exam	X	X		X		X		X	X
Vital Signs	X	X		X		X		X	X
Blood & Urine Sampling a	X	X		X ^		X		X ^	X
Urine Pregnancy Test b	X			X		X		X	X
6-minute Walk Distance			X			X			X
KCCQ Questionnaire		X				X			X
CHQ-SAS Questionnaire		X				X			X
AEs and SAEs		X	X	X	X	X	X	X	X
Electrocardiogram		X d							
Echocardiogram c		X				X			
Review Home BG Testing Results in T2D			X	X	X	X		X	X
Home Urine Ketone Testing, if Indicated			X	X	X	X		X	X
Study Drug Dispensing		X				X			
Study Drug Returned						X			X
T2D Education	X								
Heart Failure Education	X								

aAdmission tests: For screening purposes we will use available laboratory results during current admission (chemistry including eGFR, HbA1c, urine studies), additional testing will be necessary to meet all the baseline lab requirements such as serum magnesium, NT-proBNP, ketones (patients with T2D at investigator's discretion), albumin/creatinine ratio, random urine sodium , at baseline (prior to discharge). Follow up testing at 12 and 26 weeks; other ^blood tests at 6 and 20 weeks and urine culture will be performed at investigator's discretion. bUrine pregnancy test for women with childbearing potential at investigator's discretion c Echocardiogram during hospital admission (or within 6 months prior to index hospitalization) and at 12 weeks follow up visit. All visits have a +/-7-day visit window. d the most current ECG during admission. e Randomization can be performed prior to discharge or up to 7 days after discharge (if discharge planning over the weekend. \*\*COVID-19: For modified study visit options applicable during the time period of the COVID-19 emergency, please see appendix B.

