## **Measurements During follow-up:**

1. Clinical Outcomes:
  - a. Hospital readmissions, emergency department / urgent clinic visits for HF management and death (See appendix A: Heart Failure Hospitalization, ER visit and urgent outpatient clinic visit)
2. Glycemic control:
  - a. Mean daily fasting and pre-meal blood glucose levels.
  - b. HbA1c concentration at 12 and 26 weeks (T2D patients)
  - c. Number of hypoglycemic events
    - i. Clinically significant hypoglycemia defined as a BG < 54 mg/dl
    - ii. Symptomatic hypoglycemia defined as an event with typical symptoms (i.e., sweating, palpitation, and feeling of hunger) with or without confirmation by plasma glucose <70 mg/dl (3.9 mmol/L).
    - iii. Severe hypoglycemia defined as episodes necessitating assistance and associated with measured plasma glucose < 40 mg/dl (2.2 mmol/L) or with prompt recovery after administration of carbohydrates, glucagon, or other resuscitative actions. These episodes may be associated with sufficient neuroglycopenia to induce seizure or coma. Blood glucose measurements may not be available during such an event, but neurological recovery attributable to the restoration of BG to normal is considered sufficient evidence that the event was induced by low plasma glucose.
3. T2D treatment:
  - a. Number of patients receiving insulin therapy, dosage, and compliance.
  - b. Use of other oral agents, dosage, and compliance.
4. Blood pressure and heart rate
  - a. The most recent documented blood pressure (BP) of the day of screen can be used to determine enrollment eligibility. At randomization, the seated BP will be recorded in both the left and the right arms. Blood pressure (BP) and heart rate (HR) will be measured after the patient has been sitting and resting for at least 5 minutes. The arm with the highest seated systolic BP readings will be the one used for all subsequent readings (preferred arm).
5. Orthostatic blood pressure
  - a. Supine BP and pulse- The supine BP and pulse must be measured prior to the standing BP and pulse. After the patient rests in the supine position for at least 5 minutes, supine BP and pulse will be determined in the preferred arm

b. Standing BP and pulse - After the supine BP and pulse measurements are obtained, the patient will stand for 2 to 3 minutes. Standing BP and pulse will be determined from the preferred arm.

All readings must be recorded. For study analyses, the average of the BP and pulse readings will be used.

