### **Withdrawal Criteria**

1. The subject may withdraw at will at any time.
2. The subject may be withdrawn from the trial at the discretion of the investigator due to a safety concern or if judged non-compliant with trial procedures or included in contravention to the inclusion and/or exclusion criteria.
3. Adverse events (AE), i.e., any clinical, laboratory abnormality or concurrent illness which, in the opinion of the investigator, indicates that continued participation in the study is not in the best interest of the patient.
4. Doubling of serum creatinine above the baseline value confirmed by a repeated measurement within one week (study medication can be discontinued and continue study visits as described in the premature treatment discontinuation).
5. Pregnancy or intention to become pregnant.

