## **Safety**

### **Potential risks associated with dapagliflozin use:**

**Hypoglycemia.** It is possible that following the proposed protocol, T2D patients receiving basal insulin or dapagliflozin alone or in combination with antidiabetic treatment may develop hypoglycemia (< 54 mg/dl). The frequency of hypoglycemia in patients with T2D treated with dapagliflozin is expected to be < 10%. The number of reports of hypoglycemia will be analyzed statistically. For this analysis, hypoglycemia is defined as a capillary and/or laboratory BG <70 mg/dl, and clinically significant hypoglycemia a BG < 54 mg/dl. Severe hypoglycemia is defined as an event with symptoms consistent with hypoglycemia in which the subject required the assistance of another person and blood glucose less than 40 mg/dl.

**Volume depletion.** SGLT2-is, including dapagliflozin may cause intravascular volume contraction. Treatment with SGLT2-i leads to increased diuresis, which may result in a modest reduction in blood pressure. The risk of volume depletion is enhanced when two diuretics are used in combination, especially with the use of loop diuretics. Therefore, the drug should be given with caution in patients with volume depletion and hypotension. In this trial, we will exclude patients with hemodynamic shock with systolic blood pressure <100 mm Hg after initial fluid resuscitation.

**Hypotension.** SGLT2-is, including dapagliflozin may cause natriuresis and intravascular volume contraction that may lead a modest reduction in blood pressure. The risk of hypotension may be higher in elderly patients with renal impairment receiving two diuretics and the use of loop diuretics. In this trial, we will exclude patients with systolic blood pressure <100 mm Hg and during therapy, diuretic and/or antihypertensive drugs may need to be adjusted in patients with blood pressure < 100 mmHg.

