## **Laboratory Test Result Abnormalities**

The following laboratory test result abnormalities will be captured on the non-serious AE CRF page or SAE Report Form as appropriate:

- Any laboratory test result that is clinically significant or meets the definition of an SAE
- Any laboratory test result abnormality that required the subject to have study drug discontinued or interrupted
- Any laboratory test result abnormality that required the subject to receive specific corrective therapy.

It is expected that wherever possible, the clinical rather than laboratory term would be used by the reporting investigator (e.g., anemia versus low hemoglobin value).

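### No blood pressure is scheduled until week 6 and no on-treatment creatinine is required until week 12, so early silent hypotension and creatinine rises are found only by choice or through usual care

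*Combined protocol and SAP*

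**What the plan says.** Schedule of Clinic and Phone Visits gives five in-person visits after discharge. The Schedule of Assessments and Appendix B place them at weeks 2, 6, 12, 20 and 26. At week 2 the table marks the walk test, adverse-event review, home glucose review and ketone testing if indicated. It does not mark weight, physical examination, vital signs or blood. Those rows are first marked after randomization at week 6. Footnote a sets follow-up laboratory testing at weeks 12 and 26, and adds that "blood tests at 6 and 20 weeks and urine culture will be performed at investigator's discretion".

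The protocol elsewhere treats these measurements as important:

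- Potential risks associated with dapagliflozin use says that "The risk of volume depletion is enhanced when two diuretics are used in combination, especially with the use of loop diuretics", and that "during therapy, diuretic and/or antihypertensive drugs may need to be adjusted in patients with blood pressure < 100 mmHg".
- Safety Variables names as of special interest "volume depletion (defined as hypotension, syncope, orthostatic hypotension or dehydration"). It also lists "Acute kidney injury (defined as doubling of serum creatinine based on the RIFLE criteria").
- Withdrawal Criteria includes "Doubling of serum creatinine above the baseline value confirmed by a repeated measurement within one week", with permission to stop the drug and continue visits. Renal disorders asks for a re-test within a week after a rise of 50% or more, and then leaves matters to the investigator.
- Measurements During follow-up describes seated and orthostatic methods ("The supine BP and pulse must be measured prior to the standing BP and pulse") but ties the orthostatic readings to no visit.
- The separate Volume depletion section promises close monitoring of at-risk patients, including their electrolytes and kidney function, without naming a test or a date.

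**The concern.** These patients have just been discharged after decompensated heart failure. They may be up to 90 years old, with GFR as low as 25, and their standard treatment includes diuretics and other drugs that act on pressure or the kidney. They then start a drug that the protocol says may contract volume, lower pressure and raise creatinine. Low pressure without symptoms, or a creatinine rise without symptoms, exists for the trial only if someone measures it.

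A site that follows the schedule to the letter sees the patient at week 2 and takes no blood pressure. It need not take a creatinine until nearly half the treatment period has passed. Until then, detection depends on local habit and on whether a care visit happens to supply a value, so it can differ between patients and sites. Two things are at stake: the chance to adjust background drugs in time, and an early safety summary based on the same measurements in everyone.

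**Working it through.** The plan states no figure to reproduce here. The check is a reading of the schedule plus day counts.

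**Column check.** In the blood-sampling row, the two entries carrying the discretion mark fall in the week-6 and week-20 columns, which are the weeks footnote a names. The columns are therefore aligned as read. The last column combines the week-24 phone contact and the week-26 visit, which Appendix B separates. This does not touch the early visits.

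**Marks at the five in-person visits after discharge**

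| Week | Weight and vital signs | Blood |
|---|---|---|
| 2 | not marked | not marked |
| 6 | marked | discretionary |
| 12 | marked | required |
| 20 | marked | discretionary |
| 26 | marked | required |

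Vital signs are scheduled at 4 of 5 visits, and the one omitted is the earliest. Required on-treatment blood falls at 2 of 5. Creatinine is taken to be part of the chemistry in footnote a and of the clinical chemistry under Laboratory assessments.

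**Timing.** Days run from the week-0 randomization/discharge visit. Treatment lasts 26 × 7 = 182 days, and every visit has a window of ±7 days.

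- First scheduled pressure now: 6 × 7 = day 42; 42/182 = 23%; window day 35 to 49.
- With the change: 2 × 7 = day 14; 14/182 = 8%; window day 7 to 21.
- First required creatinine now: 12 × 7 = day 84; 84/182 = 46%; window day 77 to 91, and 91/182 = 50%.
- With the change: 6 × 7 = day 42; 23%; window day 35 to 49, and 49/182 = 27%.
- Required on-treatment creatinine values go from 2 to 3, and in-person visits with vital signs from 4 to 5.

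**COVID-19 period.** Appendix B allows week 6 by phone. The first scheduled pressure then moves to week 12 (day 84), or later if that window is extended. Week 2 remains an office visit there, so a week-2 measurement would still be obtained.

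**What an extra measurement would produce.** Under Adverse Events based on examinations and tests, deterioration in mandated laboratory values or vital signs is an adverse event only if it meets a seriousness criterion or is the reason for stopping the drug. Otherwise it appears in the summaries of mandated results. Accompanying signs or symptoms are reported in their own right. A low week-2 pressure without symptoms would therefore usually be recorded, available for action and summarised, but not counted as an event of special interest. Laboratory Test Result Abnormalities is broader for blood results ("Any laboratory test result that is clinically significant or meets the definition of an SAE"), but it too operates only once a value exists. I use the narrower rule, which is less favourable to the point.

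**The case against.** The best reply is that the monitoring exists outside the table. The Volume depletion section is a firm commitment, and it names loop diuretics, so it covers the patients of most concern. Appendix B says week 2 usually coincides with heart failure follow-up. Hypoglycemia risk protection adds contact every two weeks, Unscheduled Visits allows extra visits, and adverse events are reviewed at each contact. Symptomatic events and admissions will be captured. All of this stands, and many patients will have an early pressure or creatinine from usual care. But none of these sections sets a time for either measurement or requires a care value to be recorded as study data. They narrow the gap unevenly and do not close it.

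It can also be said that the protocol gives no time course for these effects and calls the pressure reduction modest, that the rule for pressure below 100 mmHg is permissive, and that the renal rules seldom force a change. Renal disorders even continues 10 mg if eGFR falls below 25. These points are fair. They limit the renal part to a secondary matter and rule out any estimate of missed events.

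A reader might infer that special-interest events are being lost and that an added measurement would recover them. The reporting rule for mandated tests does not support that. Nor should the schedule be read as leaving patients unmonitored until week 6 or week 12. It leaves two measurements unscheduled.

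**Conclusion.** The point holds as a gap in scheduled safety measurement, and it is worth correcting because the correction is cheap. The first scheduled pressure is at day 42 and could be at day 14. The first required creatinine is at day 84 and could be at day 42. Blood pressure is the main part, because the protocol itself foresees acting on a low value. The renal part is smaller: what is lost is mainly an early, even look at creatinine, and values before week 6 would still come from clinical care.

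The benefit is timely detection for clinical action and a systematic early summary. A reader might go further and infer bias between arms, since discretionary tests can follow symptoms. The trial is double-blind and nothing in the documents shows that testing would differ by arm, so this is not claimed. The primary endpoint does not depend on these measurements and is unaffected.

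The conclusion rests on three assumptions: that sites follow the schedule as written, that creatinine belongs to the required chemistry, and that days count from the week-0 visit.

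**What to change.** 1. Mark vital signs and weight at the existing week-2 visit: seated pressure and pulse at minimum, with orthostatic readings by the method already under Measurements During follow-up where feasible.
2. Make creatinine/eGFR and electrolytes required at week 6. If that visit is by phone, use the laboratory requisition that Appendix B already provides.

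This needs a schedule amendment but no new visit. Seated readings alone take about 5 minutes of rest. The full method takes at least 5 seated + 5 supine + 2 standing = 12 minutes before handling time, for patients who also do a walk test that day. The blood cost is one panel per patient, at most 392, and fewer where sites already test at week 6. Some additional re-tests under Renal disorders should be expected.

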## **Drug Dispensing Scheme**

Three bottles of dapagliflozin 10 mg or matching placebo will be dispensed by investigational pharmacy at randomization and at the 12-week clinic visit. Each bottle containing 35 tablets.

## **Rescue therapy**

Patients with T2D will be discharge on pre-admission oral agents and or insulin therapy except for sulfonylureas or TZDs. Dose of OADs and/or insulin will be adjusted as an outpatient to achieve and maintain a fasting BG between 80-140 mg/dl and a random BG < 180 mg/dl.

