#### Admission HbA1c between 8% and 10%:

- **Patients receiving OAD treatment prior to admission:**
  - Start study medication (dapagliflozin or placebo) once daily
  - If no contraindications, re-start OADs prior to admission (metformin, DPP-4 inhibitors)
  - Hold sulfonylureas or insulin secretagogues if HbA1c < 8.0%. If HbA1c >8%, reduce dose of sulfonylurea and insulin secretagogues by 50% or stopped according to physician discretion.
- **Patients receiving OAD and insulin combination prior to admission:**
  - Start study medication (dapagliflozin or placebo) once daily
  - If no contraindications, re-start OADs prior to admission, except for sulfonylureas, insulin secretagogues or thiazolidinedione (as described above).
  - Discharge patient on basal insulin at 50% of daily hospital dose.
- **Patients receiving basal bolus insulin treatment prior to admission:**

- Start study medication (dapagliflozin or placebo) once daily
- Discharge on basal insulin at 50% of hospital dose or 75% of pre-admission daily insulin dose.

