#### Admission HbA1c > 10%:

- **Patients receiving OAD treatment prior to admission:**
  - Start study medication (dapagliflozin or placebo) once daily
  - If no contraindications, re-start OADs prior to admission (metformin, DPP-4 inhibitors)
  - If HbA1c >10%, reduce dose of sulfonylurea and insulin secretagogues by 50%.
  - Insulin naïve patients prior to admission, reduce TDD of hospital insulin dose by 25%.
- **Patients receiving OAD and insulin combination prior to admission:**
  - Start study medication (dapagliflozin or placebo) once daily
  - If no contraindications, re-start OADs prior to admission, except for sulfonylureas, insulin secretagogues or thiazolidinedione.
  - In patients receiving insulin prior to admission, reduce TDD of hospital dose by 25%.
- **Patients receiving basal bolus insulin treatment prior to admission:**
  - Start study medication (dapagliflozin or placebo) once daily
  - Discharge on basal insulin at 50% of hospital dose or 75% of pre-admission daily insulin dose.

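### The Rescue therapy section excludes sulfonylureas at discharge, but the HbA1c discharge algorithm gives half dose, with no stop option, to patients on oral agents only with HbA1c above 10%

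*Combined protocol and SAP*

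**What the plan says.** All places are in the combined protocol and SAP.

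- *Rescue therapy*: "Patients with T2D will be discharge on pre-admission oral agents and or insulin therapy except for sulfonylureas or TZDs". No HbA1c level or prior regimen limits this. A separate sentence then covers outpatient dose adjustment.
- *Admission HbA1c > 10%*, patients on oral antidiabetic drugs (OAD) only: "If HbA1c >10%, reduce dose of sulfonylurea and insulin secretagogues by 50" per cent. Unlike the lower groups, this line has no option to stop. The same list says that insulin-naive "patients prior to admission, reduce TDD of hospital insulin dose by 25" per cent.
- *Admission HbA1c > 10%*, patients on OAD plus insulin: "re-start OADs prior to admission, except for sulfonylureas, insulin secretagogues or thiazolidinedione". Their insulin rule is: "In patients receiving insulin prior to admission, reduce TDD of hospital dose by 25" per cent.
- *Admission HbA1c between 8% and 10%*, OAD only: "Hold sulfonylureas or insulin secretagogues if HbA1c < 8.0" per cent, then "If HbA1c >8%, reduce dose of sulfonylurea and insulin secretagogues by 50% or stopped according to physician discretion".
- *Admission HbA1c between 6.5% and 8%*: hold below 7.0%; above 7%, halve or stop at the physician's discretion.
- *Treatment Protocol, Inpatient T2D Treatment*: study drug is added to the pre-admission regimen on the day of discharge. No sulfonylurea exception is mentioned. Patients with T2D receive insulin while in hospital.

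**The concern.** A site discharging a patient on oral agents only, with admission HbA1c above 10% and a sulfonylurea before admission, has one instruction to leave the drug out and another to give half of it. The protocol does not say which takes precedence. Two sites could send the same kind of patient home on different background therapy and each be following the text.

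Hypoglycemic events are listed as of special interest under *Safety Variables*, and change in HbA1c in T2D patients is a secondary outcome. The stake is therefore patient safety and consistent background glucose-lowering treatment in the diabetes subgroup.

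**Working it through.** The plan states no figure to reproduce here. The check sets the rules side by side and expresses each as a share of the pre-admission sulfonylurea dose.

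**Step 1. Sulfonylurea dose at discharge.** Exclusion, hold or no restart = 0%. Halving = 100% − 50% = 50%.

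| Admission HbA1c and prior treatment | Algorithm | Rescue therapy | Can both be followed? |
|---|---|---|---|
| 6.5–8%, value below 7.0% | 0% | 0% | Yes |
| 6.5–8%, value above 7% | 50%, or stop | 0% | Only if the physician stops |
| 8–10%, OAD only, value above 8% | 50%, or stop | 0% | Only if the physician stops |
| 8–10%, OAD plus insulin | 0% (not restarted) | 0% | Yes, on the operative words |
| Above 10%, OAD only | 50% | 0% | **No** |
| Above 10%, OAD plus insulin | 0% (not restarted) | 0% | Yes |

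One row is a flat contradiction, and two agree only through physician discretion. Rescue therapy names sulfonylureas but not other insulin secretagogues, so the strict conflict concerns sulfonylureas.

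**Step 2. The third wording.** The Treatment Protocol sentence adds study drug to the pre-admission regimen and names no exception. Read alone, it matches neither Rescue therapy nor the algorithm.

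**Step 3. The hold in the 8–10% group.** Values below 8.0% and values from 8% to 10% have no overlap, so this instruction is never triggered. This assumes that the HbA1c meant is the admission value that defines the group; no other is named there. The parallel hold in the lowest group (below 7.0% within 6.5–8%) can be reached.

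**Step 4. The boundaries.** Exactly 8% belongs to two groups. Within the 8–10% group it meets neither the below-8.0% nor the above-8% condition; today it is covered only by the above-7% rule of the group below. Exactly 7.0% meets neither condition in the lowest group.

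**Step 5. Insulin in the above-10%, OAD-only list.** Reducing hospital insulin by 25% leaves 100% − 25% = 75% of the hospital daily dose. Because T2D patients receive insulin in hospital, the list appears to send insulin-naive patients home on new insulin together with half-dose sulfonylurea. Discharge on insulin is implied, not stated.

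**The case against.** The strongest reply is that the algorithm sits under a heading that calls its contents treatment recommendations at discharge and gives the HbA1c-specific detail, while the other sentence is a one-line general statement under *Rescue therapy*. A site could reasonably follow the detailed rule. That softens the practical effect but does not remove the conflict: the Rescue therapy sentence sets the discharge regimen, whatever its heading, and the protocol nowhere says that the specific rule overrides it.

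A second reply is that the unreachable hold changes no patient's treatment, and that a value of exactly 8% already receives halve-or-stop through the group below. Both points stand. The hold remains a drafting error, and possibly a sign that another threshold was meant.

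Third, a reader might infer that the above-10% group contradicts itself, because OAD-plus-insulin patients also receive 75% of hospital insulin but no sulfonylurea. The documents do not support that. The two lists cover patients with different prior regimens, and the pairing of new insulin with a sulfonylurea is only implied. It is a question for the clinical team.

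Fourth, there are safeguards: outpatient dose adjustment, review of home glucose readings, and recording of the use and dosage of oral agents. These count. The two-weekly contact mentioned under *Hypoglycemia risk protection* should not be relied on. The schedule of assessments lists weeks 2, 6, 8, 12, 16, 20 and 24, and Appendix B adds week 26, so gaps reach 4 weeks, including the one from week 2 to week 6.

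**Conclusion.** The text is wrong as written, and the issue is minor. For OAD-only patients with admission HbA1c above 10% who took a sulfonylurea, the two rules give 0% and 50% of the prior dose and cannot both be followed. In the lower groups, the half-dose rules are consistent with Rescue therapy only if the physician stops the drug. The below-8.0% hold is dead text, provided that it refers to admission HbA1c.

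The documents give no count of affected patients, so none is estimated. A reader might take the expected hypoglycemia rates (below 10% of dapagliflozin-treated patients; 20% to 30% of those on basal insulin plus study drug) as the size of the harm. They do not measure it: the two groups overlap, and neither rate isolates sulfonylurea use.

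Nor does the inconsistency bias the treatment comparison. The same rules apply in both blinded arms, and randomization is blocked by diabetes status. The primary endpoint and power are unaffected. The case for correction is hypoglycemia safety and uniform background therapy.

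**What to change.** Let one rule govern; the clinical team chooses which.

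- **Option A, keep the algorithm.** Reword the Rescue therapy exception to: *except TZDs; sulfonylureas and other insulin secretagogues are handled only by the HbA1c discharge algorithm*. In the above-10%, OAD-only list, add the physician-discretion stop that the lower groups already have. The clinical team should confirm whether the drug must stop when the patient goes home on insulin. In the Treatment Protocol sentence on the pre-admission regimen, add: *as modified by the HbA1c discharge algorithm*.
- **Option B, keep Rescue therapy.** Change all three HbA1c groups to stop sulfonylureas and other secretagogues, and add the same exception to the Treatment Protocol sentence.

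Under either option, use non-overlapping groups (6.5 to <8%, 8 to 10%, >10%) and delete the below-8.0% hold, after confirming that no other threshold was intended. Under option A, also write the halve-or-stop conditions as ≥8% in the middle group and ≥7% in the lowest, so that exactly 8.0% and exactly 7.0% are covered.

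The cost is a protocol text amendment and a notice to the sites. Sample size, visits and analysis do not change.
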